10.5 Analysis Populations

[figure not shown]
10.5.1 Efficacy Analysis Population

The ITT population will serve as the population for the efficacy analysis. All randomized participants will be included in this population. Participants will be analyzed in the treatment group to which they are randomized.

10.5.2 Safety Analysis Population

The APaT population will be used for the analysis of safety data in this study. The APaT population consists of all randomized participants who received at least 1 dose of study treatment. Participants will be analyzed in the treatment group corresponding to the study treatment they actually received for the analysis of safety data using the APaT population. For most participants this will be the treatment group to which they are randomized. Participants who take incorrect study treatment for the entire treatment period will be included in the treatment group corresponding to the study treatment actually received. Any participant who receives the incorrect study treatment for one cycle but receives the correct treatment for all other cycles will be analyzed according to the correct treatment group and a narrative will be provided for any events that occur during the cycle for which the participant is incorrectly dosed.

At least one laboratory or vital sign measurement obtained subsequent to at least one dose of study treatment is required for inclusion in the analysis of each specific parameter. To assess change from baseline, a baseline measurement is also required.

10.6 Statistical Methods

10.6.1 Statistical Methods for Efficacy Analyses

This section describes the statistical methods that address the primary objective.

10.6.1.1 Objective Response Rate

The primary efficacy endpoint ORR is defined as the proportion of participants in the analysis population who have a best response of complete response (CR) or partial response (PR) based on RECIST 1.1 by investigator determination.

ORR will be estimated by treatment group. 95% CI for ORR will be provided using the Clopper-Pearson method.

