2.1 Initial Treatment Phase

As of Amendment 03, the study will be unblinded after the last participant completes Week 9 imaging assessment for efficacy analysis. Participants can choose to discontinue from the study or continue study treatment as per protocol after discussion with the investigator and if they are receiving clinical benefit. For those participants remaining in the study, procedures are simplified. The SoA has been amended to show only the required assessments.

Study Period	Screening Phase	Treatment Cycles (3-Week Cycles)					EOT	Post Treatment	Notes
Treatment Cycle	Screening (Visit 1)	1	2	3	4	5 to 35	DC	Safety Follow-up ¹	Participants who discontinue study treatment for whatever reason will proceed directly to EOT and Safety Follow-up.
Scheduling Window (Days):	-42 to -1	+3	±3	±3	±3	±3	Time of DC	30 Days from the last dose (+7 days)	
Administrative Procedures									
Informed Consent Form	X								
Inclusion/Exclusion Criteria	X								
Participant Identification Card	X								
Demographics and Medical History	X								
Prior/Concomitant Meds	X	X	X	X	X	X	X	X	
Obtain Randomization Number and Study Drug Assignment using IVRS/TWRS	X								
Scrotonin Syndrome Information Card		X							
Subsequent Anti-neoplastic Therapy Status							X	X	
Clinical Procedures / Assessments									
Review Adverse Events	X	X	X	X	X	X	X	X	Report all AEs (NSAEs and SAEs) occurring within 90 days after the last dose of study treatment, or 30 days after the last dose of study treatment if a new anti-cancer therapy is initiated, whichever is earlier.

Study Period	Screening Phase	Treatment Cycles (3-Week Cycles)					EOT	Post Treatment	Notes
Treatment Cycle	Screening (Visit 1)	1	2	3	4	5 to 35	DC	Safety Follow-up ¹	Participants who discontinue study treatment for whatever reason will proceed directly to EOT and Safety Follow-up.
Scheduling Window (Days):	-42 to -1	+3	±3	±3	±3	±3	Time of DC	30 Days from the last dose (+7 days)	
Full Physical Exam	X						X		
Directed Physical Exam		X	X	X	X	X		X	
Vital Signs, Height, and Weight	X	X	X	X	X	X	X		Height at Screening only.
12-Lead ECG with QTc Measurement	X	X*	X*				X		At Screening and DC for all participants. *At select centers, also perform on C1D1 and C2D1 at predose and 2 hr ± 15 mins after morning dose of epacadostat/placebo.
ECOG Performance Status	X	X	X	X	X	X	X		Perform within 14 days prior to randomization.
Laboratory Procedures / Assessments: Analysis Performed by Local Laboratory									

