Study treatment is defined as pembrolizumab + epacadostat or pembrolizumab + matching epacadostat placebo, and will be given for up to 35 cycles or until disease progression, unacceptable toxicity, or Investigator decision. Participants who discontinue treatment will

discontinue from the study after Safety Follow-up. Investigators will assess the images using RECIST 1.1 (see Section 9.2.1.5) to determine eligibility at screening as well as ORR after the first on-study imaging at Week 9. Tumor imaging will be site-assessed for PD and treatment discontinuation.

Specific procedures to be performed during the trial, as well as their prescribed times and associated visit windows, are outlined in the Trial SoA - Section 2. Details of each procedure are provided in Section 9 – Study Assessments and Procedures.

There is no interim analysis in this study. During the course of the study, the external Data Monitoring Committee (eDMC) will perform 1 safety review based on the eDMC charter.

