9.2.1.1 Initial Tumor Imaging

Note: As of Amendment 03, central review of imaging is no longer applicable. This section has been updated accordingly.

Initial tumor imaging at Screening must be performed within 28 days prior to the date of randomization. The site study team must review screening images to confirm the participant has measurable disease per RECIST 1.1.

Tumor imaging performed as part of routine clinical management are acceptable for use as screening tumor imaging if they are of diagnostic quality and performed within 28 days prior to the date of randomization.

If brain imaging is performed to document the stability of existing metastases, MRI should be used if possible. If MRI is medically contraindicated, CT with contrast is an acceptable alternative.

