9.2.1.2 Tumor Imaging During the Study

Note: As of Amendment 03, central review of images and iRECIST are no longer applicable. After the first on-study imaging assessment at Week 9, further imaging will be performed as per local SoC guidelines however the data will not be collected. This section has been updated accordingly.

The first on-study imaging assessment should be performed at 9 weeks (63 days \pm 7 days) from the date of randomization. No further imaging is mandated; any further imaging for disease assessments will be performed by site investigator/radiology assessment as per local SoC guidelines; only the date of scans performed as per SoC needs to be documented in the eCRF. Imaging timing should follow calendar days and should not be adjusted for delays in cycle starts. If the bone scan is positive at baseline, bone scans should be performed as per local SoC guidelines; the results will not be monitored, only the date of scans performed as per SoC needs to be documented in the eCRF.

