9.2.1.3 End of Treatment and Follow-up Tumor Imaging

Note: As of Amendment 03, there is no protocol specified imaging after the Week 9 assessment for efficacy analysis. This section has been updated accordingly.

For participants who discontinue study treatment before the Week 9 imaging assessment for efficacy analysis, tumor imaging should be performed at the time of treatment discontinuation (\pm 4 week window). If previous imaging was obtained within 4 weeks prior to the date of discontinuation, then imaging at treatment discontinuation is not mandatory. For participants who discontinue study treatment due to documented disease progression, this is the final required tumor imaging.

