10.2 Responsibility for Analyses/In-House Blinding

The statistical analysis of the data obtained from this study will be the responsibility of the Clinical Biostatistics department of the Sponsor.

The IVRS vendor/Sponsor will generate the randomized allocation schedule(s) for study treatment assignment for this protocol, and the randomization will be implemented in IVRS.

This study will be conducted as a double-blind study under in-house blinding procedures. The official, final database will not be unblinded until medical/scientific review has been performed, protocol deviations have been identified, and data have been declared final and complete.

An eDMC will be convened to review accumulating safety data. The eDMC responsibilities and review schedules will be outlined in the DMC charter.

Blinding to treatment assignment will be maintained at all investigational sites until the last participant completes the first scheduled imaging (ie, Week 9) for efficacy analysis. Participant-level unblinding will be restricted to an external unblinded statistician and external unblinded scientific programmer performing the analysis, who will have no other responsibilities associated with the study. The extent to which individuals are unblinded with respect to the results will be documented. Additional logistical details, revisions to the above plan, and data monitoring guidance will be provided in the DMC Charter.

Prior to final study unblinding, the unblinded statistician and unblinded scientific programmer will not be involved in any discussions regarding modifications to the protocol, statistical methods, identification of protocol deviations, or data validation efforts.

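### Does the primary ORR need a written rule for which scans count toward best response?

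*Combined protocol and SAP*

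**What the plan says.** The Synopsis, Section 4 and SAP Sections 10.4.1.1 and 10.6.1.1 give the same definition: the "proportion of participants in the analysis population who have a best response of complete response (CR) or partial response (PR", judged by the investigator under RECIST 1.1. None of them names a visit, a day window or a confirmation requirement.

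The timing is given elsewhere:

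- Section 5.1 has investigators apply RECIST 1.1 "to determine eligibility at screening as well as ORR after the first on-study imaging at Week 9".
- Section 10.2 keeps sites blinded "until the last participant completes the first scheduled imaging (ie, Week 9) for efficacy analysis", and Section 10.1 places the final analysis after the last participant's Week 9 scan.
- Section 9.2.1.2 sets that scan at 63 days, plus or minus 7, from randomisation. After it, "further imaging will be performed as per local SoC guidelines however the data will not be collected".
- Section 9.2.1.3 covers early stoppers. For those "who discontinue study treatment before the Week 9 imaging assessment for efficacy analysis, tumor imaging should be performed at the time of treatment discontinuation", with 4 weeks allowed either side. It adds a waiver: "If previous imaging was obtained within 4 weeks prior to the date of discontinuation, then imaging at treatment discontinuation is not mandatory". Section 2.1 lists this scan among the efficacy measurements and requires it only when treatment stops before Week 9.
- Section 7.2.2 excludes Second Course responses from the primary analysis.
- Section 10.5.1 puts every randomised participant in the efficacy population, and Section 10.8 states that no hypothesis is tested.

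**The concern.** A best response implies choosing among assessments, yet the endpoint text does not say which assessments are in the set. Three kinds of scan seem to lack a rule.

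1. **Discontinuation scans.** Section 2.1 says: "Participants who discontinue study treatment for whatever reason will proceed directly to EOT and Safety Follow-up". For these participants the discontinuation scan takes the place of Week 9, but its window is four times as wide on each side (28 days against 7).
2. **The scan that replaces it under the waiver.** The waiver does not say the previous imaging must be post-baseline. Section 9.2.1.1 says: "Initial tumor imaging at Screening must be performed within 28 days prior to the date of randomization". A very early stopper could therefore meet the waiver with the baseline scan alone.
3. **Other recorded results.** Section 9.9.5.5 has assessments at unscheduled visits recorded. The superseded text of Section 9.9.5.2 shows a 9-weekly imaging schedule, so later results may have been entered before Amendment 03.

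ORR by arm is the only efficacy output. If the rule were chosen after unblinding, it could be chosen with responses by arm in view. A reader might also set a first-scan rate beside the 21.1% monotherapy ORR that the protocol cites from a study with 18.5 months' median follow-up, without seeing that the two rest on different observation times.

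**Working it through.** **Step 1: reproduce the plan's figures.** Inputs are n = 42 per arm and the responder counts in Table 12 (Section 10.9), with the Clopper-Pearson 95% method of Section 10.6.1.1. The lower limit is the 0.025 quantile of Beta(x, n − x + 1); the upper limit is the 0.975 quantile of Beta(x + 1, n − x).

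| x/42 | ORR | Computed 95% CI | Table 12 |
|---|---|---|---|
| 9 | 21.4% | 10.3, 36.8 | 10.3, 36.8 |
| 10 | 23.8% | 12.1, 39.5 | 12.0, 39.4 |
| 11 | 26.2% | 13.9, 42.0 | 13.9, 42.0 |
| 12 | 28.6% | 15.7, 44.6 | 15.7, 44.6 |

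Three rows agree exactly. The 10/42 limits are 12.05 and 39.45 to two decimals, so the printed row is 0.1 point low at each end, a rounding slip with no consequence.

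**Step 2: size of a counting choice.** One participant counted differently moves an arm's ORR by 1/42 = 2.4 points, two by 2/42 = 4.8 and three by 3/42 = 7.1. Three would take 9/42 = 21.4% to 12/42 = 28.6%, the span of Table 12. The interval at 9/42 is 36.8 − 10.3 = 26.5 points wide. The number affected is not in the documents; zero to three is an assumption for illustration.

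**Step 3: how far a discontinuation scan can stray from Week 9.** The Week 9 window is 63 ± 7, or day 56 to 70. For a stop on day d the discontinuation window is d − 28 to d + 28. It ends by day 70 whenever d ≤ 70 − 28 = 42, so only stops after day 42 can give a scan later than the Week 9 window. A stop on day 62 gives day 34 to 90, ending 20 days late. That participant is, however, already inside the Week 9 window when treatment stops.

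**Step 4: the waiver and the baseline scan.** A baseline scan b days before randomisation meets the waiver as worded when d + b ≤ 28. With b = 1 this needs d ≤ 27; with b = 14, d ≤ 14; with b = 28, d ≤ 0. The case can arise, but response is change from baseline, so a baseline scan cannot show CR or PR. The participant has no response and stays in the denominator under Section 10.5.1, as a non-responder.

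**Step 5: what each kind of scan can do to the ORR.**

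| Scan | What the plan gives | Can the choice alter the ORR? |
|---|---|---|
| Week 9 | Section 5.1 ties ORR to it | No open choice |
| Discontinuation scan before Week 9 | An efficacy measurement, required only when Week 9 was not reached | Only if it shows CR or PR; someone stopping for progression seen on that scan has PD on it |
| Baseline scan under the waiver | Not a response assessment | No |
| Standard-of-care scan after Week 9 | Date only | No |
| Second Course | Excluded | No |
| Unscheduled scan | Recorded; no explicit rule | Only if it alone shows CR or PR |
| Later result entered before Amendment 03 | Existence inferred; no count given | Only if it alone shows CR or PR |

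**Step 6: confirmation.** No section requires a response to be confirmed, and one mandated post-baseline scan could not supply confirmation. The unconfirmed reading is the only workable one.

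**The case for a change.** The best case for a change is that ORR is the whole efficacy result and the repair would be cheap. The sponsor wrote an explicit exclusion for Second Course responses, so the silence on discontinuation and unscheduled scans stands out. Two analysts could treat a response entered at a later scan before Amendment 03 differently: the best-response wording, with only the Second Course excluded, would let it in, while Section 5.1 would leave it out. Sections 10.1 and 10.2 do not settle this, because they time the analysis and the unblinding and do not select a participant's scans. The protocol also says, in the retained iRECIST rationale, that responses to pembrolizumab can come late, so a Week 9 rate should not be read as a mature ORR.

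Part of this stands. The text does leave a small choice for a few possible scans, and whoever reports the result should describe it as an early, unconfirmed rate. What does not follow is a risk to the result. Section 5.4.1.1 has images read blinded to treatment. Section 9.1.11 asks for imaging data to be entered before unblinding. Section 10.2 holds the database blinded until deviations are identified and the data are declared final. One rule would apply to both arms, and there is no test whose error rate could suffer. The Week 9 timing is stated often enough in the protocol that an informed reader would not take the figure for a long-follow-up ORR.

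**Conclusion.** No change is needed. The endpoint sections are terse, but the protocol as a whole supplies the working rule: the Week 9 scan or, for those who stopped before it, the discontinuation scan, with everyone else in the denominator as a non-responder. The baseline-scan and denominator questions cannot alter an ORR. What remains is the handling of unscheduled assessments and of later results entered before Amendment 03. The existence of the latter is inferred, and no count is given for either.

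Each such participant would be worth 2.4 points in one arm, within an interval at least 26.5 points wide over the range of Table 12, in a study that only estimates. The interval is valid whichever single rule is used. The conclusion assumes that analysts settle these few cases at the data review that Section 10.2 places before unblinding, which is ordinary practice. It also assumes about 42 participants per arm, as in Section 10.9. If the data showed many responses resting only on scans outside this set, the question would carry more weight; nothing in the documents suggests that.

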10.6.2 Statistical Method for Safety Analysis

Safety and tolerability will be assessed by clinical review of all relevant parameters including adverse experiences (AEs), laboratory tests, and vital signs.

Individual events and the broad AE categories consisting of the proportion of participants with any AE, a drug-related AE, a serious AE, an AE which is both drug-related and serious, a Grade 3-5 AE, a drug related Grade 3-5 AE, a fatal AE, dose interruption due to an AE and discontinuation due to an AE, will be summarized by counts and percentages by treatment group (Table 11).

Table 11 Analysis Strategy for Safety Endpoints

Safety Endpoint	Descriptive Statistics
Any AE	X
Any Serious AE	X
Any Grade 3-5 AE	X
Any Drug-Related AE	X
Any Serious and Drug-Related AE	X
Any Grade 3-5 and Drug-Related AE	X
Dose Interruption due to AE	X
Discontinuation due to AE	X
Death	X
Specific AEs, SOCs	X
Change from Baseline Results (Laboratory toxicity grade)	X

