3.3.3 Benefit/Risks for the Combination of Epacadostat and Pembrolizumab

The combination of pembrolizumab and epacadostat has the potential to cause more frequent, more severe, and/or new immune-related toxicities as compared with each agent individually.

Study INCB 24360-202 (KEYNOTE-037) is an ongoing Phase 1/2 study of epacadostat administered in combination with pembrolizumab. Phase 1 is being conducted in participants with advanced or metastatic solid tumors who have disease progression on at least 1 line of therapy for advanced or metastatic cancer (except melanoma). Phase 2 is conducted in participants with NSCLC, melanoma, TCC of the genitourinary tract, triple negative breast cancer, SCCHN, ovarian cancer, Diffuse Large B-Cell Lymphoma, clear cell renal cell cancer, gastric cancer, hepatocellular carcinoma, and microsatellite instability (MSI) high colorectal cancer.

Safety data is available on 294 participants from the Phase 2 portion of INCB 24360-202 (KEYNOTE-037) treated with the recommended Phase 2 dose of epacadostat 100 mg BID and pembrolizumab 200 mg Q3W. The most frequently reported ($\geq 10\%$) treatment-related AEs of any grade were fatigue (29%), rash (17%), nausea (11%), and pruritus (10%). Rash includes the preferred terms rash, rash generalized, rash macular, rash maculopapular, and rash pruritic. Treatment-related AEs Grade ≥ 3 were observed in 18% of participants. The most common

treatment-related AEs Grade \geq 3 were increased lipase (4%) and rash (3%). There was one treatment-related death due to respiratory failure which was secondary to aspiration pneumonia.

Given initial data observed in KEYNOTE-037 suggesting improved efficacy of pembrolizumab with epacadostat and an overall safety profile comparable to anti-PD-1 monotherapy, this combination represents a rationale and promising option in participants with metastatic UC.

4. Objectives/Hypotheses and Endpoints

NOTE: As of Amendment 03, the primary endpoint of the study will be ORR based on RECIST 1.1 as assessed by the investigator. All other efficacy endpoints, including imaging, will no longer be collected or performed after the first imaging assessment at Week 9. This section has been updated accordingly.

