In male/female participants of at least 18 years of age with histologically confirmed diagnosis of advanced/unresectable or metastatic UC that has recurred or progressed following one prior line of platinum-containing chemotherapy for advanced/metastatic disease:

Objective/Hypothesis	Endpoint
Primary	

Objective: To estimate the objective response rate (ORR) of pembrolizumab plus epacadostat and pembrolizumab plus placebo based on RECIST 1.1 by investigator determination.	
ORR - defined as the proportion of participants in the analysis population who have a best response of complete response (CR) or partial response (PR).
Secondary	

Objective: To evaluate the safety and tolerability of pembrolizumab plus epacadostat versus pembrolizumab plus placebo.	
Adverse events (AEs)Study drug discontinuations due to AEs.

5. Study Design

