9.3.7 Events of Clinical Interest (ECI)

Selected non-serious and serious adverse events are also known as Events of Clinical Interest (ECI) and must be reported to MSD.

Events of clinical interest for this trial include:

1. an overdose of study treatment, as defined in Section 9.4 – Treatment of Overdose, that is not associated with clinical symptoms or abnormal laboratory results.
2. an elevated AST or ALT lab value that is greater than or equal to 3X the upper limit of normal and an elevated total bilirubin lab value that is greater than or equal to 2X the upper limit of normal and, at the same time, an alkaline phosphatase lab value that is less than 2X the upper limit of normal, as determined by way of protocol-specified laboratory testing or unscheduled laboratory testing.*

*Note: These criteria are based upon available regulatory guidance documents. The purpose of the criteria is to specify a threshold of abnormal hepatic tests that may require an additional evaluation for an underlying etiology. The trial site guidance for assessment and follow up of these criteria can be found in the Investigator Trial File Binder (or equivalent).

3. serotonin syndrome. The signs and symptoms of serotonin syndrome are described in Section 7.2.1.1.

ECIs that occur after the consent form is signed but before treatment randomization must be reported by the Investigator to MSD if the event caused the participant to be excluded from the study or is the result of a protocol-specified intervention.

All ECIs that occur from the time of treatment randomization through 90 days following cessation of study treatment, or 30 days following cessation of treatment if the participant initiates new anticancer therapy, whichever is earlier, must be reported by the investigator to MSD within 24 hours of learning of the event.

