10.1 Statistical Analysis Plan Summary

NOTE: As of Amendment 03, this section has been updated.

Key elements of the SAP are summarized below; the comprehensive plan is provided in Section 10.2 through Section 10.12.

Study Design Overview	This is a randomized, double-blind, multicenter Phase III trial to evaluate the efficacy and safety of pembrolizumab plus epacadostat compared to pembrolizumab plus placebo in participants with UC of the renal pelvis, ureter, bladder, or urethra that is transitional cell type or mixed histology (predominantly transitional cell) type (KEYNOTE-698/ECHO-303).
Treatment Assignment	Approximately 85 participants will be randomized 1:1 to receive pembrolizumab + epacadostat or pembrolizumab + placebo. Stratification factors are provided in Section 7.3.1.
Analysis Populations	Efficacy: Intention-to-Treat (ITT) Safety: All Participants as Treated (APaT)
Primary Endpoints	Objective Response Rate (ORR) per RECIST 1.1 assessed by investigator determination
Statistical Methods for Key Efficacy Analyses	ORR will be estimated by treatment group with 95% CI calculated by the Clopper-Pearson exact method [Clopper, C. J. and Pearson, E. S. 1934]
Statistical Methods for Key Safety Analyses	Point estimates (count and percentage) by treatment group will be provided for safety endpoints.
Interim and Final Analyses	There will be no interim analysis. During the course of the study, DMC will perform 1 safety review based on the DMC charter. The final analysis will be performed after the last participant completes the Week 9 imaging assessment.
Multiplicity	There will be no multiplicity adjustment.
Sample Size and Power	Total sample size is approximately 85.

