10.4.2 Safety Endpoints

Safety and tolerability will be assessed by clinical review of all relevant parameters including AEs, SAEs, fatal AEs, laboratory tests, and vital signs as described in Section 9.5. Furthermore, specific events will be collected and designated as ECIs as described in Section 9.3.7.

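### The secondary objective compares safety between arms, but the SAP plans no between-arm difference or interval and no pooled immune-related AE rate

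*Combined protocol and SAP*

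**What the plan says.** - **Objective.** Section 4 and the Synopsis give the secondary objective as "To evaluate the safety and tolerability of pembrolizumab plus epacadostat versus pembrolizumab plus placebo". Its two listed endpoints are AEs and study drug discontinuations due to AEs.
- **Method.** The summary in Section 10.1 states: "Point estimates (count and percentage) by treatment group will be provided for safety endpoints". Section 10.6.2 says that individual events and the broad AE categories "will be summarized by counts and percentages by treatment group (Table 11". Neither place mentions a difference between arms or a confidence interval.
- **Table 11 rows.** Any AE; serious; Grade 3-5; drug-related, alone and combined with serious or Grade 3-5; dose interruption; discontinuation; death; "Specific AEs, SOCs"; and change in laboratory toxicity grade. No row groups immune-related AEs, and Section 10 contains no definition or term list for them.
- **Anticipated risk.** Section 3.3.3 says the combination "has the potential to cause more frequent, more severe, and/or new immune-related toxicities as compared with each agent individually".
- **Events of clinical interest.** Section 10.4.2 adds that "specific events will be collected and designated as ECIs as described in Section 9.3.7". Section 9.3.7 names three: overdose without symptoms or abnormal laboratory results, a composite liver-test criterion, and serotonin syndrome. Section 10.6.2 does not say how designated ECIs will be summarised.
- **Inference.** Section 10.8 states that no hypotheses will be tested. Section 10.6.1.1 nevertheless gives ORR a 95% Clopper-Pearson interval in each arm.

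**The concern.** The primary objective asks for an ORR estimate in each arm, and the per-arm method matches it. The safety objective is worded as a comparison, yet its method is also per-arm and, unlike ORR, carries no measure of precision.

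Two things are at stake. First, percentages side by side at about 42 per arm can be over-read either way: similar figures as reassurance, a small gap as harm. Second, the number a reader most needs about this combination is the proportion of participants in each arm with any immune-related event, and that is not a planned output. Immune-related events would be scattered over many term-level rows. If a pooled rate is wanted later, the grouping would have to be chosen after treatment assignments are known, and that leaves it open to selection.

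**Working it through.** **1. The plan's own precision figure.** Section 10.9 takes 42 per arm, and Table 12 gives Clopper-Pearson intervals for ORR. Recomputed from beta quantiles: 9/42 gives 10.3-36.8%; 10/42 gives 12.05-39.45% (stated 12.0-39.4, a rounding difference); 11/42 gives 13.9-42.0%; 12/42 gives 15.7-44.6%. Table 12 reproduces. The plan has no equivalent figure for safety.

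**2. What a between-arm estimate would show.** Inputs: Grade 3 or higher treatment-related AEs were 18% on the combination (Section 3.3.3, the Phase 1/2 study across several tumour types) and 16.5% on pembrolizumab alone (Section 5.4, the Phase 3 urothelial study). These come from different studies and serve only as an illustration. 42 × 0.18 = 7.6, about 8; 42 × 0.165 = 6.9, about 7.

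- Difference: 8/42 − 7/42 = 19.05% − 16.67% = +2.4 points.
- Wilson 95% limits: 8/42 gives 9.98% to 33.30%; 7/42 gives 8.32% to 30.60%.
- Newcombe lower limit: 2.38 − √[(19.05 − 9.98)² + (30.60 − 16.67)²] = 2.38 − 16.63 = −14.2.
- Newcombe upper limit: 2.38 + √[(33.30 − 19.05)² + (16.67 − 8.32)²] = 2.38 + 16.52 = +18.9.

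The Wald half-width for a common rate p is 1.96 × √[2p(1 − p)/42]. It is 12.8 points at p = 10%, 15.9 at 16.5%, 19.6 at 30% and 20.8 at 61.3% (the any-grade treatment-related rate on pembrolizumab in Section 5.4).

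**3. Why a pooled immune-related rate cannot be recovered.** Take a hypothetical arm of 42 with 4 participants under one immune-related term and 3 under another. The number with at least one of the two lies anywhere from 4 (full overlap) to 7 (none), that is 9.5% to 16.7%. Each further term widens the possible range. Organ-class rows do not help, because they mix immune-related with other events and cut across the immune-related group.

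**4. How thin single terms can be.** At an assumed true rate of 3%, 42 × 0.03 = 1.26 cases are expected per arm, and the chance of none is 0.97^42 = 0.28. An assumed pooled rate of 20-30% would give 42 × 0.20 = 8.4 to 42 × 0.30 = 12.6 participants. Not every row is sparse: any-grade rash at 17% (Section 3.3.3) gives 42 × 0.17 = 7.1.

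**The case against.** The strongest reply is that the descriptive plan is deliberate and disclosed. Enrolment stopped early, the scope was cut to preliminary data, no hypotheses are tested, and the ORR analysis itself gives no difference between arms. The objective is to evaluate safety, and its two endpoints both have Table 11 rows by arm in a blinded, randomised study. Anyone can compute a risk difference from those counts, and the interval will be too wide to settle anything.

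Much of this stands. A reader might infer that the plan cannot address its comparative safety objective at all. The documents do not support that: side-by-side counts from randomised arms are a partial comparison. A reader might also infer that the ECIs go unanalysed. That is too strong as well. Serotonin syndrome and symptom-free overdose have their own event terms and would appear among the individual events. Sites report the liver event against its composite criteria (Section 9.3.7), so counting it does not depend on single-parameter laboratory tables. What is missing is only a statement that designated ECIs will be tabulated.

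The reply does not dispose of two things. A descriptive difference with an interval is estimation, just as the ORR intervals are, and needs no test or multiplicity adjustment; a small sample is a reason to print the interval. And although a risk difference can be derived later from published counts, a pooled immune-related rate cannot.

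**Conclusion.** The point holds as a modest, inexpensive improvement. For an objective worded as a comparison, the SAP plans neither a between-arm estimate nor an interval, and it specifies no participant-level immune-related AE rate although the protocol names that toxicity as the combination's risk.

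The imprecision left unstated is roughly 13 to 21 points either side of a difference for event rates between 10% and 61%; the worked example is +2.4 points with a 95% CI of about −14 to +19. This rests on 42 per arm, a projection from Section 10.9 (the treated population used for safety may be slightly smaller), and on rates borrowed from two different studies. The 3% term rate and the 20-30% pooled rate are assumptions. The additions would make the uncertainty visible; they would not establish whether the arms differ in safety.

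**What to change.** In Section 10.6.2 and Table 11:

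1. Add the between-arm risk difference with a 95% CI (for example Newcombe or Miettinen-Nurminen) for the broad AE categories, labelled descriptive and without any test.
2. Add rows for any immune-related AE and any Grade 3-5 immune-related AE, counted once per participant, by arm, with the same difference and interval. Define them by a closed preferred-term list fixed before the unblinding described in Sections 7.4 and 9.1.11. The categories of Table 3 in Section 7.2.1 will not serve as they stand: that is a management table, and its catch-all for other immune-related events has no term list and needs a judgement of cause.
3. As a minor clarification, state that site-designated ECIs (Section 9.3.7) will be tabulated by arm, with the liver ECI cross-checked against concurrent AST/ALT, bilirubin and alkaline phosphatase values, which Appendix 4 already requires.

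The cost is some SAP wording, a few table rows, and a term list to be agreed before unblinding, which takes real clinical and coding effort. The intervals will be wide and must be presented as descriptive. No new data are needed.
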